6.3. Baseline patient characteristics

Demographic and other baseline data will be summarized descriptively for both the SS and the FAS. The list of baseline patient characteristics to be summarized is:

	Variables	Type of variables
Medical/Surgical History:	Diagnoses. Medical and surgical treatments.	Categorical nominal
Recent Medication Prior to First Dose of IMP	The relevant medication at the time of the IC signature will be obtained from each patient at the time of screening and before the first IMP dose.	Categorical nominal
Demographic information	Gender Age Race	Categorical nominal Continuous Categorical nominal
Leukemia Diagnosis and Prior Cancer Therapy	Initial leukemia diagnosis. Screening diagnosis	Categorical nominal
Sokal Risk Score	Sokal risk score	Continuous
ECOG	ECOG Performance Status(0, 1, 2, 3, 4, 5)	Categorical ordinal
Vital signs	Temperature. Pulse. Respiratory rate. Blood pressure	Continuous
Weight and Height	Height (cm). Body weight (Kg; 1 decimal)	Continuous
Physical Examination and Extra-medullary Leukemia Involvement	Examination of general appearance, skin, neck (including thyroid), eyes, ears, nose, throat, lungs, heart, abdomen, back, lymph nodes, extremities, vascular and neurological. Findings on physical examination consistent with extra-medullary leukemic involvement will be recorded (e.g., lymph nodes, liver, and spleen size).	Categorical nominal
Blood Samples for BCR-ABL Molecular Response Assessment	Percent ratio of BCR-ABL transcripts versus control gene transcripts converted to IS	Continuous
Complete Blood Count with Differential	Peripheral total white blood cell count, hemoglobin, hematocrit, platelet count, red blood cell count, leucocytes, absolute neutrophil count (ANC), and WBC differential	Continuous
Serum chemistry	sodium, potassium, blood urea nitrogen (BUN) or urea, fasting glucose, albumin, creatinine, total cholesterol, triglycerides, total bilirubin (direct and indirect, only if total bilirubin is out normal range), GOT, GPT, GGT, alkaline phosphatase, LDH, magnesium, phosphorous and calcium. Amylase and lipase determinations will be added only in screening and during bosutinib plus atezolizumab combination treatment.	Continuous
Serology	Hepatitis B serology (Hepatitis B surface antigen, Hepatitis B core antibody, and Hepatitis B surface antibody) hepatitis C and HIV	Categorical nominal
Bone Marrow Analysis and Cytogenetics	Percentage of Ph+ metaphases in the bone marrow and is defined as complete, partial, minor, minimal and none	Continuous Categorical nominal
Pregnancy Test	hCG laboratory test	Categorical nominal
12-Lead Electrocardiogram	QTcF interval	Continuous

6.4. Outcome definitions

The primary objective is to evaluate the safety profile of bosutinib 400 mg daily in combination with atezolizumab as first line treatments in participants with chronic myeloid leukemia. The safety set population will be used for all safety analyses. For a detailed description of safety variables analysis see the 6.9 Safety Data Analysis section.

➤ Secondary variables:

- Major Molecular Response (MMR) and Molecular Response (MR) rates at 3, 6, 12 months and at the End of Treatment (EoT) visit.
- Percentage of participants alive at months 6 and 12 and at the EoT visit.
- Number of confirmed MR4 and MR4.5 at end of treatment.
- The rate of confirmed MR4 and MR4.5 at the end of treatment.
- Number of Complete Cytogenetic Responses (CCyR) at 1 year]
- The rate of Complete Cytogenetic Response (CCyR) at 1 year.
- Number of days to response (CCyR, MMR, MR4, MR4.5). [Time Frame: at the EoT visit]
- The median time to response and the overall estimated probability of response (CCyR, MMR, MR4, MR4.5).
- Number of overall surviving patients [Time Frame: at the EoT visit]
- Number of progression-free survival patients.[Time Frame: at the EoT visit]
- Number of failure-free survival patients. [Time Frame at the EoT visit]
- Number of event-free survival patients. [Time Frame: at the EoT visit]
- Immunological Studies: phenotypic Assays:
 - Cell characterization: NK cells (CD3- CD56+; CD16+ CD56+; TNF α ; IFN α ; Granzyme b NK-LGL cells (CD56+ CD57+), T-LGL cells (CD3+ CD57+), CD8 TCR α/β , NK markers (NKG2D, KIR2DL2/DL3/DS2, KIR2DL5B).
 - b. Differentiation and maturation (NKG2A/CD16) and proliferation (NK67) markers of NK cells.

- c. CD4+ T cells activation markers: CD25 CD69 HLA-DR.
- d. Predictive markers of CML relapse: T regs (CD4+ CD25int-hi CD127low), CD8+ T cells (PD-1/PD-L1) and plasmacytoid dendritic cells (CD86+).

6.5. Analysis methods

Descriptive statistics are presented using mean and standard deviations for continuous variables and count and percentages for categorical variables. The 95% confidence interval (CI) for a proportion will be reported for the primary efficacy variable. The Shapiro-Wilks test will be used to test the normality of the distribution of continuous variables. Statistical differences between groups were analyzed using the chi-square test for categorical data and the Student's t test for quantitative data. Quantitative data showing non-normal distribution were analyzed using the Mann-Whitney U test. The Kaplan-Meier method is used to study survival. A p-value of <0.05 was considered statistically significant. All analyses were carried out with the free statistical program R (<https://cran.r-project.org/>).

Primary Objective:

Frequency and percentage of adverse events will be summarized by system organ class and/or preferred term, severity (based on CTCAE grades), type of adverse event and causality relation to study treatment by the study phases. 95% confidence intervals of the proportion of adverse events will be computed using the exact binomial distribution.

Secondary Objectives: The rates of molecular responses at certain time points as well as the percentages will be presented together with an exact 95% binomial confidence interval.

All time to event endpoints will be analyzed using the Kaplan-Meier method and will be presented by Kaplan-Meier method plots.

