11.5 Treatment Duration

The patients included will remain in the study for at least 100 weeks, 4 weeks (1 cycle) in the first treatment phase, 48 weeks (12 cycles) in the second treatment phase, and 48 weeks (12 cycles) in the third treatment phase), unless discontinue early.

The First 10 Patients:

- First cycle, they will receive bosutinib 400 mg/day in monotherapy.
- Second and third cycles, they will receive bosutinib 400 mg/day in combination with atezolizumab 840 mg every two weeks.
- If no safety issues are detected, these patients will cross-over from bosutinib 400 mg/day plus atezolizumab 840 mg every 2 weeks to bosutinib 400 mg/day plus atezolizumab 1680 mg every 4 weeks for 10 more cycles.
- After 12 cycles of treatment with bosutinib plus atezolizumab combination, the patients will continue with bosutinib 400 mg/day in monotherapy for 12 more cycles.

Other 26 Patients:

- First cycle, they will receive bosutinib 400 mg/day in monotherapy.
- Second cycle, they will receive bosutinib 400 mg/day plus atezolizumab 1680 mg every 4 weeks for 12 cycles.
- After 12 cycles of treatment with bosutinib plus atezolizumab combination, the patients will continue with bosutinib 400 mg/day in monotherapy for 12 more cycles.

If, at any point during the treatment with bosutinib 400 mg/day plus atezolizumab 1680 mg every 4 weeks, 2 or more patients experience DLTs, atezolizumab dosage will change to 840 mg every 2 weeks.

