Patients will continue to be closely monitoring. If DLTs appear in 2 or more patients at a dose of 1680 mg of Atezolizumab every 4 weeks, the dose of atezolizumab will be reduced for all patients to an 840 mg Atezolizumab every 2 weeks dose.

Third Therapy

All patients completing 12 treatment cycles (48 weeks) will begin the last therapy of study.

4.2. Randomization:

Randomization does not apply.

4.3. Sample size:

There will be no formal calculation of the sample size. The sample size is selected to allow sufficient data collection for the DLT and safety assessment. It is an exploratory study. The minimum number of patients for the DLT evaluation will be 10 if no DLT is observed. After MTD is calculated, 26 more patients will be recruited for the dose variation phase. 36 patients (both, a first group of 10 patients and a second of 26 patients) will receive bosutinib 400 mg/day in monotherapy during one cycle of treatment. According to previous experience, we assume that, at most, 15% of the patients included will not enter the dose escalation phase after the first month of treatment with bosutinib, due to side effects. Consequently, a total of 30-31 patients will receive the combination of bosutinib plus atezolizumab.

4.4. Statistical interim analysis and stopping guidance:

There are no interim analyses planned.

4.5. Timing of final analysis:

Primary outcome, adverse events, will be recorded continuously throughout the study, starting on the date of the first administration of the study medication, and, at least, up to the 28-day follow-up visit after the last dose of treatment.

5. Trial Population

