6.9. Safety data analysis

Reporting of safety information will be split into subsets by first phase, second phase, third phase, and fourth phase.

Adverse Events: Summary tables for adverse events (AEs) have to include only AEs that started or worsened during the on-treatment period, the treatment-emergent AEs (TEAEs). However, all safety data (including those from the pre-treatment period) will be listed and those collected during the pre-treatment period are to be flagged.

The incidence of treatment-emergent adverse events (new or worsening from baseline) will be summarized by system organ class and/or preferred term, severity (based on CTCAE grades), type of adverse event, causality relation to study treatment by the phases or subsets previously described.

Deaths reportable as SAEs and non-fatal serious adverse events will be listed by patient and tabulated by type of adverse event and safety subset.

Specific safety event categories will be considered. Such categories consist of one or more well-defined safety events which are similar in nature and for which there is a specific clinical interest in connection with the study treatment(s).

For each specified safety event category, number, and percentage of patients with at least one event part of the safety set will be reported. Also, AESI will be summarized and analyzed.

Laboratory abnormalities: For laboratory tests covered by the Common Terminology Criteria for Adverse Events (CTCAE) version 5.0 the study's biostatistician and reporting team will grade laboratory data accordingly. For laboratory tests covered by CTCAE, a Grade 0 will be assigned to all non-missing values not graded as 1 or higher. Grade 5 will not be used.

In some cases, (e.g., white blood cell differentials) the lower limits of normal ranges used in CTCAE definition have to be replaced by a clinically meaningful limit expressed in absolute counts.

For laboratory tests where grades are not defined by CTCAE, results will be graded by the low/normal/high classifications based on laboratory normal ranges.

The following by-safety subset summaries will be generated separately for hematology, and biochemistry tests:

- number and percentage of patients with clinically significant laboratory abnormalities, by parameter and worst post-baseline CTCAE grade. Each patient will be counted only for the worst grade observed post-baseline, regardless of the baseline status

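### Crude AE percentages by phase are not comparable between a 1-cycle lead-in and a 12-cycle combination period, and no exposure-based or time-based measure is planned

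*SAP*

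**What the plan says.** Under the primary objective, SAP 6.5 states that "Frequency and percentage of adverse events will be summarized by system organ class and/or preferred term", then by severity and by "type of adverse event and causality relation to study treatment by the study phases". It adds that "95% confidence intervals of the proportion of adverse events will be computed using the exact binomial distribution". SAP 6.9 states that "Reporting of safety information will be split into subsets by first phase, second phase, third phase, and fourth phase", and that "Summary tables for adverse events (AEs) have to include only AEs that started or worsened during the on-treatment period". Protocol 15.3.1 and 15.3.2 plan the same by-phase tables.

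Protocol 11.5 sets the lengths: "4 weeks (1 cycle) in the first treatment phase, 48 weeks (12 cycles) in the second treatment phase", then "48 weeks (12 cycles) in the third treatment phase". SAP 4.5 has AEs recorded at least "up to the 28-day follow-up visit after the last dose of treatment".

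Neither document plans a person-time denominator, an exposure-adjusted rate, a time-to-first-AE analysis or a comparison over equal windows. The safety paragraph of the synopsis speaks of AE incidence rates but defines no denominator, and the SAP does not take the term up. Kaplan-Meier methods appear in SAP 6.5 for survival and for the time-to-event endpoints of the secondary objectives. SAP 6.9 lists time of onset as a data item, but no planned analysis uses it.

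**The concern.** A binomial proportion has no time in it. The chance that a patient has at least one event grows with the length of the window, and the combination window is planned at 12 times the length of the lead-in.

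The trial has no control arm. Readers who want to know what atezolizumab adds to bosutinib will naturally set the phase columns side by side, and the lead-in is the only period before any atezolizumab is given. From the planned tables they could not separate added toxicity from longer observation. The exact intervals would not warn them, and could seem to confirm a difference that duration alone produced.

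**Working it through.** **The plan's own figures.** 36 × (1 − 0.15) = 30.6, which agrees with the 30-31 patients expected to enter the combination (Protocol 15.5, SAP 4.3). 4 + 48 + 48 = 100 weeks, as in Protocol 11.5.

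**Inputs.** Lead-in 1 cycle and combination 12 cycles (Protocol 11.5); 36 and about 31 patients. The AE risk per cycle, p, is not given, so it is an assumption and is varied.

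**Constant hazard, no added toxicity.** Crude incidence over c cycles is 1 − (1 − p)^c.

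| Assumed p per cycle | Lead-in, 1 cycle | Combination, 12 cycles | First-event rate per 100 patient-cycles, both periods: −100 × ln(1 − p) |
|---|---|---|---|
| 1% | 1.0% | 11.4% | 1.0 |
| 2% | 2.0% | 21.5% | 2.0 |
| 3% | 3.0% | 30.6% | 3.1 |
| 5% | 5.0% | 46.0% | 5.1 |
| 10% | 10.0% | 71.8% | 10.5 |

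At p = 5%, a typical result is 2/36 (exact 95% interval 0.7% to 18.7%) against 14/31 (27.3% to 64.0%). With no true difference, the two exact intervals fail to overlap, combination higher, with probability 0.21 at p = 2%, 0.52 at 3% and 0.87 at 5%. These probabilities treat the two groups as independent, which is a simplification because they are largely the same patients.

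**Early stopping.** If the mean combination exposure were only 6 cycles, p = 5% gives 1 − 0.95^6 = 26.5% against 5.0%. Stopping narrows the gap but does not close it.

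**Front-loaded onset.** Take a Weibull hazard from day 1 with shape k and 5% incidence in the lead-in. The combination then covers cycles 2 to 13, and its cumulative hazard is (13^k − 1) times that of the lead-in.
- k = 0.75: combination 25.9%
- k = 0.5: 13^0.5 − 1 = 2.61, so 1 − 0.95^2.61 = 12.5%
- Equal percentages when 13^k = 2, that is k = ln 2 / ln 13 = 0.27
- k = 0.25: combination 4.5%, so the direction has reversed

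**A rate on its own.** In the k = 0.5 case the lead-in rate is 5.1 per 100 patient-cycles. The combination rate is about 5.13 × 2.61 / 12 = 1.1, a ratio of about 0.22. Again no toxicity was added, yet now the combination looks more than four times safer.

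**Phase definitions.** SAP 6.9 names four phases without boundaries; Protocol 11.5 has three. If the four are lead-in, 840 mg every 2 weeks, 1680 mg every 4 weeks and final bosutinib, the first 10 patients would have 1, 2, 10 and 12 cycles. At p = 5% the first three give 5.0%, 9.8% and 40.1%, so the windows remain unequal.

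**Denominator.** It is not stated for later phases. With all 36 patients kept in, 46.0% becomes 46.0 × 31/36 = 39.6%.

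**The case against.** The strongest reply is that these are legitimate descriptive tables. The study is exploratory, the primary objective is to describe the combination's safety profile, and no AE test between phases is specified. Within a phase, a percentage with an exact interval is a valid summary. This stands, and it is why the remedy adds to the tables and removes nothing.

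A reader might infer that the crude percentages are bound to be biased against the combination. The documents do not support that. The direction rests on a roughly constant hazard, and no AE risk per cycle is given. The nearest figure in the plan points to early toxicity: at most 15% of patients are expected not to go on after the first month because of side effects. A constant 15% per cycle would mean losing 1 − 0.85^12 = 86% over 12 cycles, so constancy should not be presumed.

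A reader might also infer that lead-in against combination is the only internal evidence on what atezolizumab adds. It is not. The final bosutinib period has the same planned 12 cycles (up to about 13 with follow-up), so duration bias against it is small. DLT assessment and causality by phase also bear on the question. The final period is not a clean comparator, however. Only patients completing the combination enter it (Protocol 9.4), and atezolizumab's 27-day terminal half-life (Protocol 6.3) carries exposure into it.

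Finally, a Poisson rate is no neutral correction, because it too assumes a constant hazard and can mislead the other way. This also stands, and it shapes the fix.

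**Conclusion.** The point holds as a matter of comparability. Lead-in and combination percentages cover windows of 1 and 12 cycles and cannot be compared directly as planned. Under an assumed constant risk of 2% to 5% per cycle with no added toxicity, the gap from duration alone is 2% v 22% to 5% v 46%. It is smaller with early-onset events, vanishes near a Weibull shape of 0.27 and reverses below that. The accurate statement is that the combination can look worse through longer observation, not that it will. The risks and shapes are illustrative assumptions. The unequal windows and the absence of any exposure-based or time-based AE measure come from the documents themselves. This is a worthwhile and inexpensive improvement to the primary safety reporting; the crude percentages remain valid within each phase.

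**What to change.** Keep the crude percentages and, in SAP 6.5 and 6.9, add for each phase:

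1. The number of patients entering the phase, used as the denominator, and the patient-cycles at risk.
2. First-event rates per 100 patient-cycles with exact Poisson intervals, for all TEAEs, grade 3 or higher events and AESIs.
3. For the same categories, time to first event shown as cumulative incidence, or the lead-in cycle set against the first combination cycle. This is needed because the rates in item 2 assume a constant hazard.

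Reconcile the four phases in SAP 6.9 and Protocol 15.3.1 with the three therapies in Protocol 11.5, and state the rule that assigns an AE to a phase, including events in the 28 days after the last dose. This has to be settled before the new tables can be programmed.

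The cost is a little more programming. Bosutinib intake is recorded in a diary (Protocol 11.2.1), atezolizumab is given on site, and AE onset relative to dosing is already a listed item (SAP 6.9), so no new data are needed. The one downside is that the Poisson rates must not be read alone; a footnote on the tables should say so.

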Medicinal product for Human Use or Investigational Drug	Any substance or combination of substances presented as having properties for treating or preventing disease in human beings or which may be used in or administered to human beings either with a view to restoring, correcting or modifying physiological functions by exerting a pharmacological, immunological or metabolic action, or to making a medical diagnosis (Royal Decree 1090/2015, of 4 December).
Loss of Complete Hematologic Response	Loss of CHR is defined as the appearance of any of the following, confirmed by a second determination ≥ 4 weeks later (unless associated with progression to AP/BC or CML-related death): 
• WBC count that rises to $> 20.0 \times 10^9/L$;• Platelet count that rises to $\geq 600 \times 10^9/L$;

	
• Progressing hepatosplenomegaly to a size \geq 5 cm below the left intercostal margin;• Appearance of \geq 5% myelocytes + metamyelocytes in the peripheral blood;• Appearance of blasts or promyelocytes in the peripheral blood.
Molecular Response (MR)	
• MMR – BCR-ABL \leq 0.1% (IS).• MR4 – BCR-ABL \leq 0.01% (IS).• MR4.5 \leq 0.0032% (IS).• UNDETECTABLE.
Overall Survival (OS)	OS is calculated from the first day of therapy to the date of death. Surviving patients will be censored at the time of the last follow-up.
Subject Number	A unique identifying number assigned to each patient who enrolls (i.e. signs the IC) in the study.
Per-Protocol Set (PPS)	A subset of the full analysis set (FAS) who is compliant with the clinical study protocol (i.e. Composed by subjects that have not incurred in major protocol deviations that could jeopardize the validity of the data and the study outcomes).
Premature Patient Withdrawal	When a subject exits from the study prior to the planned completion of all study treatment administration and/or assessments or procedures. From this time, all study treatment administration is discontinued and no further assessments or procedures will be done, other than the monitoring for progression and/or survival.

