Progression Free Survival (PFS)	Progression free survival (PFS) is defined as the time from the date of first treatment administration until the time of disease progression. Subjects who die without a reported progression will be considered to have progressed on the date of their death. Subjects who do not progress nor die will be censored on the date of their last hematological assessment.
Safety Set (SS)	Composed by all subjects who received at least one dose of study medication.
Study Treatment	Includes any drug or combination of drugs in any study arm administered to the subject as part of the required study procedures.
Trial Subject	An individual who participates in a clinical trial, either as recipient of an investigational medicinal product or as a control.
Variable	Identifier used in the data analysis; derived directly or indirectly from data collected using specified assessments at specified time points.

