15.4.2 Analyses Methods for Secondary Objectives

A descriptive analysis of the secondary objectives will be carried out. Qualitative variables will be summarized by counts and percentages. Quantitative variables will be summarized by means of mean, standard deviation, minimum, maximum and main quartiles. The 95% confidence intervals will also be calculated.

The hypothesis of normality will be tested by the Shapiro-Wilk test. A repeated measurement ANOVA or its equivalent non-parametric test will be used depending on the result of this test. The qualitative variables will be analyzed by means of the Fisher Chi-square test/exact test or Cochran's Q test, as appropriate.

Survival analysis will be performed using the Kaplan-Meier estimation method and the Log-rank test. A p-value of <0.05 will be considered statistically significant.

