5.3. Withdrawal/follow-up

Patients may suspend their participation in the study whenever they wish, based on his/her own judgement and opinion, without giving any explanation, although the investigator may investigate the reasons of a voluntary dropout.

The investigator may also decide to withdraw a patient from the trial if he/she does not comply with the protocol, due to AEs or treatment inefficacy or toxicity.

Patients who do not comply with at least 70% of the scheduled doses of bosutinib or that, in 4 or more times, the administration of atezolizumab is cancelled, will be withdrawn from the study.

6. Statistical Principles

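### Kaplan-Meier is prescribed for time to response with no censoring or competing-event rule and no analysis set; if withdrawn non-responders are censored, on-study response is overstated

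*SAP*

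**What the plan says.** SAP 6.5 names one method for this class of endpoint: "All time to event endpoints will be analyzed using the Kaplan-Meier method and will be presented by Kaplan-Meier method plots". Protocol 15.4.2 agrees: "Survival analysis will be performed using the Kaplan-Meier estimation method and the Log-rank test". SAP 6.4 lists among the secondary variables "The median time to response and the overall estimated probability of response (CCyR, MMR, MR4, MR4.5"), so time to response falls under that rule. Neither document names a competing-event estimator.

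SAP 5.3 lets the investigator withdraw a patient who "does not comply with the protocol, due to AEs or treatment inefficacy or toxicity". It also requires withdrawal for less than 70% of scheduled bosutinib doses or four or more cancelled atezolizumab administrations. Protocol section 4 (Premature Patient Withdrawal) says that from then on "no further assessments or procedures will be done, other than the monitoring for progression and/or survival". Response is not on that list.

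Protocol section 4 gives censoring rules for OS ("Surviving patients will be censored at the time of the last follow-up") and PFS ("Subjects who do not progress nor die will be censored on the date of their last hematological assessment"). Time to response has none.

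Other provisions that bear on the point:
- The FAS is limited to patients who complete the combination, and the PPS is a subset of it (protocol 15.1, SAP 6.2). Protocol 11.6 ties efficacy to the PPS. The SAP assigns no set to the secondary endpoints.
- SAP 6.6 applies last-observation-forward and next-observation-backward to time-to-event endpoints, without saying whether this continues after withdrawal.
- SAP 6.5 reports molecular response rates at fixed times as proportions with exact binomial intervals.

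**The concern.** Kaplan-Meier gives a censored patient the later response rate of those still under observation. That suits a patient who is event-free when follow-up ends for unrelated reasons. It does not suit one withdrawn "due to AEs or treatment inefficacy or toxicity", whose on-study response can no longer occur or be seen. Censoring such patients makes one minus Kaplan-Meier (1-KM) larger than the proportion who responded on study, and the median time to response comes out too short or appears reached when it was not.

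The trial's rationale is that the combination deepens molecular response. A single-arm figure of this kind is likely to be read beside monotherapy results such as the 47% one-year MMR cited in protocol 6.2. A figure that depends on unstated handling of leavers cannot be read that way. The sensitivity analysis in SAP 6.7 would not expose the problem, because restricting to complete data drops the same patients.

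**Working it through.** **The plan's own figure.** 36 x (1 - 0.15) = 30.6, which matches the 30-31 patients expected to receive the combination (protocol 15.5, SAP 4.3). No response probability, power or event count is stated, so nothing else can be reproduced.

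**Inputs from the documents.** 36 treated; at most 15% (5.4) leaving after cycle 1; 47% (116/246) one-year MMR on bosutinib; RT-qPCR visits at D29, 85, 169, 253, 337, 449, 533, 617 and 700.

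**Assumptions.** A constant response hazard; the early leavers are non-responders who go just after D29; all later withdrawals. Calculations use expected counts.

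**Whole-number illustration.** Take 17 responders among 36, with 6 leaving before any response.
- Cumulative incidence: 17/36 = 47.2%; median not reached.
- 1-KM with the 6 censored: 17/(36 - 6) = 56.7%; median reached.
- Gap: 9.4 points. With 5 leavers, 17/31 = 54.8%, a gap of 7.6.

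**All 36 treated, 15% leaving after cycle 1.** Hazard = -ln(1 - 0.47)/337 = 0.001884 per day.
- 1-KM: 47.0% at D337; 1 - exp(-0.001884 x 700) = 73.3% at D700.
- Responders by D29: 36 x 0.0532 = 1.91. Still at risk: 36 - 1.91 - 5.4 = 28.69.
- Cumulative incidence at D337: [1.91 + 28.69 x (1 - exp(-0.001884 x 308))]/36 = (1.91 + 12.63)/36 = 40.4%.
- Cumulative incidence at D700: [1.91 + 28.69 x (1 - exp(-0.001884 x 671))]/36 = (1.91 + 20.58)/36 = 62.5%.
- Median on the visit grid: at D449, 1-KM is 57.1% and cumulative incidence 48.9%. Kaplan-Meier puts the median at D449; cumulative incidence puts it one visit later, at D533 (54.2%).

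**Summary of gaps (1-KM minus cumulative incidence, in points).**

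| Set and withdrawals | D337 | D700 |
|---|---|---|
| 36 treated, 5.4 after cycle 1 | 6.6 | 10.8 |
| plus 3 in the combination phase (assumed) | 8.9 | 16.0 |
| plus 6 in the combination phase (assumed) | 12.0 | 21.7 |
| FAS of 25, 2 leaving in third therapy (assumed) | 0 | 3.0 |
| FAS of 22, 3 leaving in third therapy (assumed) | 0 | 5.1 |
| Withdrawn non-responders kept at risk to EoT | 0 | 0 |

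On the FAS, patients who leave before completing the combination never enter the curve, so nothing is censored before D337. The overstatement remains: in the whole-number illustration, if the 30 who stay complete the combination, the FAS figure is again 17/30 = 56.7%, this time because the 6 were excluded.

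**The case against.** The strongest reply is that the plan never says withdrawn patients are censored for response. SAP 6.6, read literally, carries a withdrawn patient's non-response forward, and the gap is then zero. That stands as a possible reading, so the bias is conditional. But the same sentence speaks of repeated-measures data with missing follow-up, and carrying a later value backward needs a later value, which fits intermittent gaps better than permanent withdrawal. With Kaplan-Meier prescribed and no further response data, censoring at the last assessment is what an analyst would do by default.

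Second, on the FAS or PPS most leavers are absent, so the effect of the estimator is small. That also stands, and it moves most of the problem to the set definition.

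Third, treating withdrawal as a competing event is a choice of estimand. Withdrawn patients receive further CML treatment (protocol 12.20) and may respond later. This is fair: cumulative incidence with withdrawal as a competing event describes response on study treatment and should be labelled so.

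Fourth, the primary objective is safety and the study is exploratory. True, and it limits the importance of the point.

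A reader might infer that the trial's response results as a whole will be inflated by ten points or more. The documents do not support that. The larger gaps need all 36 patients as the set, censoring at withdrawal, and a loss at the stated ceiling or beyond, and the fixed-time molecular response rates do not use Kaplan-Meier. Nor do the calculations measure any extra bias from poor responders being the ones who leave: withdrawal for inefficacy is discretionary, and the figures assume leavers had the same hazard as the rest.

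**Conclusion.** The gap in the plan is real: Kaplan-Meier is the only method given for time to response and overall probability of response, with no censoring rule, competing-event rule or analysis set, while withdrawal can be for toxicity or inefficacy and ends response assessment.

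If withdrawn non-responders are censored and all 36 treated patients are analysed, the plan's 15% ceiling alone overstates on-study response by about 7 points at D337 and 11 at D700, and by more with later withdrawals. In the FAS or PPS, censoring adds nothing at D337 and about 3 to 5 points at D700, and the main overstatement comes from excluding early leavers. Only the 36, 15%, 30-31, 47% and visit days come from the documents; the constant hazard and every later withdrawal are assumed. The point concerns secondary, descriptive endpoints and should be settled before analysis.

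**What to change.** In SAP 6.5, for CCyR, MMR, MR4 and MR4.5:
- Name the set: all treated patients, or all who start the combination. Changing the estimator while keeping the completers-only FAS or PPS would leave most of the overstatement in place.
- Estimate by cumulative incidence (Aalen-Johansen), with withdrawal before response, progression to AP/BC and death as competing events.
- Read the median time to response from that curve, and report it as not reached if the curve stays below 50%.
- Label the quantity as response while on study treatment.

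In SAP 6.6, state that the carry-forward and carry-backward rule does not apply after withdrawal. Keep Kaplan-Meier for OS and PFS, whose censoring rules are already written, and leave the exact binomial fixed-time rates as they are.

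Cost: SAP wording and a few lines of R, with no new data. The only real downside is a less favourable response figure.
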